9.2.1. PRIMARY OUTCOME VARIABLE

The primary outcome variable for this study will be how well the autologous fibroblasts are tolerated by the participants.

9.2.2 SECONDARY OUTCOME VARIABLES

Secondary outcome variables for this study will be 1) an increase in epidermal thickness as detected by optical coherence tomography in vivo, or by histology, and 2) an increase in KRT9 by RT-PCR, western or immunohistochemistry

9.3 EARLY STOPPING RULES

If a participant has a serious adverse event thought to be possibly, probably or definitely related to the autologous fibroblasts, we will stop and consult with the IRB and the FDA before proceeding.

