
If a subject refuses consent for the tattoo marker, but is otherwise willing to complete all other study procedures, then we can use the palpated sacral hiatus, and initiation of the gluteal cleft as 2nd and 3rd universal landmarks. In addition, we will maximize the use of individual landmarks such as nevi, seborrheic keratoses, scars and hemangiomas which are found on human skin. In previous studies that the PI has performed(1), he has used exactly this method for the injection of hyaluronic acid to identify sites months later and had universal success at identifying injection sites. Also, to enhance our ability to identify sites we will not limit injections to one side of the buttocks (or non-buttocks area as above) to enhance the available number of landmarks and ensure proper identification in subsequent visits after the injection. Finally, we will frequently also consult clinical photographs (photographed with rulers) of the injection site taken on the day of injection to optimize our ability to correctly map injection sites.

We will avoid injection into the skin above the ischial tuberosity to minimize discomfort and risks of ulcers

Phase One: Single Dose Injection

After numbing the participant with anesthesia described in Visit 2, two of the sites will be injected with 0.7-0.8 mls of media (5% DMSO, 6% hetastarch and 2.5% human serum albumin) containing 30-40 million autologous fibroblasts into a small area about 3-4mm injection area subepidermally at the level of the epidermis-

dermis junction. The third site will be injected with the same volume of media containing no autologous cells.

Phase Two: Intermittent Dosing Regimen

We do not propose to increase the total number of cells injected, but to inject fewer cells more often. At the PI's discretion, the subject may receive injections of the dosing regimen or injections of 10% DMSO.

Two of the three treated sites will receive cells. A total of 4 injections may maximally occur; the first will always include cells for these sites. The remaining 3 injections may include vehicle and up to 10% DMSO instead of cells administered within 30 days after injection of cellular product.

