The third control site will not receive cells but instead be injected with the same volume of media or up to 10% DMSO, containing no autologous cells; it, may receive intermittent administration of vehicle media or up to 10% DMSO with the same schedule as above for the two sites receiving cells. The 10% DMSO media will be RIMSO-50, a FDA-approved product for the use in interstitial cystitis and delivered intravesically. The injections may be spaced in any manner over the 30 days. The dose volume will be determined on the basis of results from Phase One. A range of dose volumes may be tested but the total number of injected autologous fibroblasts will not exceed 30-40 million. As in Phase One, the dose will be prepared by appropriately trained and qualified personnel in the cellular therapy core and administered by the PI. We will be using an FDA approved product (RIMSO-50), because we unexpectedly found in our animal studies that the DMSO in our vehicle actually enhances cellular engraftment. We propose to inject no more than 10% DMSO at a volume of less than 1 ml into the skin not more than 3 times. We will only inject the areas where the vehicle or cells were previously injected (3 approximately 6 mm circles). We confirm that this study will not proceed until this Protocol Amendment is granted approval from the Johns Hopkins Medicine Institutional Review Boards.

The following information will be recorded by the investigator administering the cells (see Cell Administration sheet in Appendix V):

- Vial identification numbers
- Date of administration
- Times of administration
- Total cell dose
- Injection sites

Superficial skin scrapings are routinely done in dermatology and may be employed before or after we inject cells in order to potentially enhance tissue repair and regeneration. They might also occur during graft evaluations in subsequent visits. Scrapes will be done at injection sites using two gentle steady strokes of a sterile disposable #15 blade or curette. This wounding technique was specifically chosen to eliminate bleeding and infection risks.

Participants will be observed for 60 minutes following the cell administration for adverse events. At two points in this interval we will perform blood pressure and pulse measurements to monitor for an allergic reaction

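### The only mandatory stop (section 9.3) names the autologous fibroblasts and was not extended to the DMSO or vehicle injections that Phase Two allows in place of cells

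*Combined protocol and SAP*

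**What the plan says.** Section 9.3 requires a halt and consultation with the IRB and FDA after a "serious adverse event thought to be possibly, probably or definitely related to the autologous fibroblasts". No other provision makes a pause compulsory.

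Section 5.2.4, under the Phase Two dosing regimen, widens what is injected:

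- At the PI's discretion, "the subject may receive injections of the dosing regimen or injections of 10% DMSO".
- At most 4 injections are given. The first always contains cells at the two cell sites. After that, "The remaining 3 injections may include vehicle and up to 10% DMSO instead of cells".
- "The third control site will not receive cells but instead be injected with the same volume of media or up to 10% DMSO". It may then be re-injected on the same schedule as the cell sites.
- The DMSO limit is "no more than 10% DMSO at a volume of less than 1 ml into the skin not more than 3 times".

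On observation, the same section says "Participants will be observed for 60 minutes following the cell administration for adverse events" and "At two points in this interval we will perform blood pressure and pulse measurements to monitor for an allergic reaction".

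Section 7.4.2 sends every serious event, whatever its cause, to the IRB and immediately to a Safety Monitor with independent power to stop the trial.

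**The concern.** Safety and tolerability is the primary objective (section 2), and participants are healthy volunteers with no expected benefit (section 6.3.1). Phase Two adds DMSO as a separate injection because animal work suggested that it helps engraftment. The product is approved for intravesical use and is here injected into skin. Section 6.1.2 reports human experience with 5% DMSO in vehicle; Phase Two allows up to 10%.

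A stop that names only the cells treats two serious events differently according to attribution. One judged at least possibly due to cells must halt the trial. One judged due to DMSO or vehicle alone leaves the halt to discretion. Nothing in the plan suggests that this difference was intended.

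**Working it through.** The plan states no figure on this point, so the check compares wording and counts exposure.

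**1. What can be injected without cells.** Inputs from section 5.2.4: 3 sites, at most 4 injections per site, 2 cell sites whose first injection always contains cells, and 1 control site that never receives them.

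- All site-injections: 3 × 4 = 12.
- Without cells, at most: control 4, plus cell sites 2 × 3 = 6, giving 10 of 12.
- One of those 10 is the control injection at the first visit, when the other two sites receive cells. The remaining 9 (3 visits × 3 sites) fall at visits that may involve no cells at all.
- How many of the 12 may be DMSO depends on how the cap of 3 is read. If it applies per site, the answer is 3 × 3 = 9. If it limits the total number of injections per participant, the answer is 3. The text does not say which.

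These are upper bounds on exposure. Use is discretionary and could be zero, and the counts do not measure harm.

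**2. Amount of DMSO per injection.**

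- Phase One: 0.7–0.8 mL × 5% = 0.035–0.040 mL.
- Same volume at the full 10%: 0.070–0.080 mL, a ratio of 2.0.
- At a ceiling of 1 mL: 1 × 10% = 0.100 mL, a ratio of 0.100/0.040 = 2.50 to 0.100/0.035 = 2.86.

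The last ratios are limits, since 5.2.4 keeps the volume below 1 mL and the concentration is a maximum.

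**3. A serious event attributed to DMSO or vehicle alone, provision by provision.**

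- 9.3, mandatory stop: not triggered as worded. Section 8.1 identifies the cultured fibroblasts as the active component, so the phrase does not readily stretch to an injection containing none.
- 7.4.2, IRB: reported, at the latest within 10 working days (deaths follow a separate policy).
- 7.4.2, FDA: reported immediately if unexpected, otherwise within 15 calendar days.
- 7.4.2, Safety Monitor: told immediately and may stop the trial.
- 6.1.2: DMSO adverse events are notified to the FDA and IRB.
- 6.2.2: monitoring for DMSO effects is promised, with no procedure, duration or stop.

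Notification is therefore complete. Only the compulsory pause is missing. On the listed injection days (30, 37, 42, 59) the gaps are 7, 5 and 17 days, so a further injection could fall due before the IRB's outer reporting limit unless someone chooses to stop.

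**4. How often attribution to DMSO alone is plausible.** Every recipient has already had cells, which remain until excision, so many events, including most systemic ones, would be called at least possibly cell-related and would trigger 9.3. What remains is mainly an acute reaction soon after a DMSO-only injection, or a reaction confined to the control site. Few reactions in a circle of about 6 mm would be serious. The documents give no rate for either.

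**The case against.** The strongest reply is that the participant is already protected. Serious events reach the IRB and a Safety Monitor regardless of cause, known DMSO allergy is an exclusion (4.2.2), and a possible relation to cells given earlier is easily conceded. The attribution scale in 7.3 refers to the investigational agent and has no separate DMSO category, which also makes attribution to DMSO alone less likely. All of this stands and keeps the point minor. It does not supply a required pause, which is what 9.3 provides for cells.

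A reader might infer that a DMSO-related serious event is not covered at all. Section 7.4.2 rules that out.

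A reader might also infer that DMSO-only visits carry no observation, because the 60 minutes are tied to cell administration. The documents do not support so firm a reading:

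- The sentence sits in 5.2.4, which covers all Phase Two injection visits (#3–6), after both regimens have been described.
- The administration sheet in Appendix V uses the same label and has rows for three injections, although one site gets no cells.
- The stated purpose is to detect allergy. The allergens listed in 4.2.2 include DMSO, albumin and hetastarch, all vehicle components, whereas the cells are the participant's own.
- The lack of a vital-signs mark at the Phase Two injection visits proves little, because the Phase One schedule is equally blank at its injection visit, where observation plainly applies.

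Staff would probably observe at every injection. What survives is that the wording does not say so.

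**Conclusion.** The point holds in a limited form. The only compulsory stop omits agents that Phase Two may inject in place of cells at up to 3 of 4 injections, and at a site that never receives cells. A serious event attributed solely to DMSO or vehicle is reported and may lead to a stop, but no pause is required. The observation wording is a matter for clarification, not a demonstrated lapse.

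Severity is minor. The number of events affected cannot be estimated from the documents and is probably small. Tallies of visits or minutes without required observation would be worst-case figures resting on the strictest reading of 5.2.4 and on an unknown number of DMSO recipients, so they should not be taken as the size of the harm. The conclusion rests on reading 9.3 as written and on DMSO actually being used in Phase Two. It affects no sample size, error rate or efficacy analysis.

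**What to change.** **Main change.** In 9.3, replace *the autologous fibroblasts* with *any study injection (cells, vehicle or DMSO)*, leaving the rest of the rule as it is. The downside is possibly a few more pauses for IRB and FDA consultation; the documents do not allow an estimate of how many.

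**Secondary clarification.** In 5.2.4, tie the 60-minute observation, with its two blood pressure and pulse checks, to *every study injection visit, including visits without cells*. The cost is at most 3 visits × 60 minutes = 3 more observation hours per participant, and nothing if staff already observe at every visit.

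Both changes fit in one amendment.

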4.1.1 BLINDING/RANDOMIZATION

The clinicians will not be blinded, but the research staff who measure epidermal thickness and KRT9 levels will be blinded. It will be impossible to blind the clinicians since they will be injecting the cells versus vehicle. Although we could blind the clinicians to the identity of volar versus non-volar cells, it might be important to judge adverse events and will not impact on endpoint determination—primarily occurring in the laboratory. Another reason not to blind the clinicians is that this is a feasibility trial.

We will blind the research staff by labeling sites/biopsies with numbers (1, 2 or 3) rather than the identity of injected cells at that location. At the injection visit, the numbers are assigned as in the CRF (see Appendix V) with the corresponding identity of cells injected by the clinician. This injection form will not be available to research staff unless there is an adverse event when un-blinding will occur. Blinding will occur for research staff both during measurements of epidermal thickness/area by OCT as well as in the laboratory phase where the removed injection sites will be analyzed by histology and RT-PCR.

The subjects will also only be told the number of each site so that subjects will be blinded as well (See Appendix VI; injection diary).

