5.2.3 SUTURE REMOVAL VISIT (VISIT #2) (STUDY DAY 14 +/- 2 DAYS)

The participant will return to clinic for suture removal. At this study visit, the following will be obtained/performed:

- Vital signs including BP, pulse, and respirations
- Biopsy site/AE assessment
- Biopsy site suture removal

The participant will be given their graft administration visit appointment at this time.

5.2.4 GRAFT INJECTION VISIT PHASE ONE VISIT #3 (STUDY DAY 30 +/- 7 DAYS) OR PHASE TWO VISITS #3-6 (STUDY DAYS 30, 37, 42, 59)

The participant will return to the clinic on or near Day 30 for their graft injection.

Participants will have the following assessments done:

- History and limited physical examination
- Females of child bearing potential will have a urine pregnancy test done prior to administration of the investigational cells to ensure that they are not pregnant.
- Clinical photographs will be taken of each of these 3 sites before the investigational product is administered. These photographs will be used throughout the study to document changes in the skin as well as aid in location of the site at subsequent visits. Photograph files will be coded with the participant's unique identifier. The participant will not be identifiable from the clinical photographs.

Together with the study investigator, a site for injection of the subject's grown fibroblasts will be chosen. The injections will be placed by the investigator into the three sites mutually identified (e.g. the three injections will be placed on one of

the participant's buttocks, or non-buttocks area as above). The injection sites will be spaced at least 5 cm from the center of any neighbor and may be divided between left and right buttocks or non-buttocks area as above to ensure a lack of overlap.

Identification of injection sites to optimize future localization will occur through these steps:

- We will identify distances and angle from anatomical landmarks such as the sacroiliac joint.
- We will draw anatomical landmark maps with transparency paper used for projections. We will circle landmarks so that the transparency can be directly placed on the subjects buttocks or non-buttocks area as above in a repeatable orientation, and also identify injection sites.

To further enhance our ability to localize injection sites, we will use a small volume of ($x < 0.025$ ml) tattoo ink to mark areas of cellular injection:

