6.1.2 DMSO INJECTION

We have been injecting 5% DMSO in vehicle with no adverse events. When used at very high doses (such as large volumes of 100%), the risks of DMSO include

bad breath, and changes in the skin (like redness, itching, hives, dryness, and rarely blisters). Very rarely people may feel sedated, have headaches or nausea. However, we have not observed any of these effects. Adverse events will be notified to the FDA and IRB.

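### The only automatic pause in the plan (9.3) is tied to the fibroblasts, so a serious event attributed solely to vehicle, DMSO or skin scraping does not require one

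*Combined protocol and SAP*

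**What the plan says.** Section 9.3 is a single sentence. A serious adverse event "thought to be possibly, probably or definitely related to the autologous fibroblasts" means that the trial stops and the IRB and FDA are consulted before it proceeds.

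Section 5.2.4 describes what else is given at the test sites. In Phase One: "The third site will be injected with the same volume of media containing no autologous cells". In Phase Two: "The third control site will not receive cells but instead be injected with the same volume of media or up to 10% DMSO". At the two Phase Two sites that do receive cells, the first injection always contains them, but "The remaining 3 injections may include vehicle and up to 10% DMSO instead of cells". On the DMSO product the section says: "The 10% DMSO media will be RIMSO-50, a FDA-approved product for the use in interstitial cystitis and delivered intravesically". Sections 5.2.4 and 5.2.5 also allow gentle scraping with a blade or curette at injection and monitoring visits; the Phase Two outline in section 3 places this in a subset of subjects.

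Section 7.3 grades attribution against the investigational agent and does not define that term. Section 7.4.2 sends all serious events to the IRB whatever their cause, reports serious events to the FDA (unexpected ones immediately by phone or fax), and notifies at once a Safety Monitor who has authority to stop the trial.

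**The concern.** The pause covers one of the exposures under test and is silent on the others. The protocol itself separates them. Section 8.1 names the cultured fibroblasts as the active component, and section 6 lists fibroblasts and DMSO injection as distinct risks with distinct mitigations. The DMSO mitigation (6.2.2) is choice of product, small volume and monitoring, with no pause.

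The DMSO step also goes beyond the experience cited for it. Section 6.1.2 says: "We have been injecting 5% DMSO in vehicle with no adverse events". Phase Two allows up to twice that concentration, injected into skin, using a product approved for delivery into the bladder.

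At stake is whether other subjects may go on being injected or scraped while a serious event is under review. They are healthy volunteers (6.2.7) with no expected personal benefit (6.3.1). That is a good reason for the pause to cover the non-cell test interventions as well.

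**Working it through.** The rule has no numerical threshold, so there is no plan figure to reproduce. The check is of wording first, then of exposure ceilings.

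**1. Does any other text require a pause?** None in the supplied documents. Section 7.4.2 requires reporting and gives the Safety Monitor power to stop. Section 6.1.2 adds that adverse events will be notified to the FDA and IRB. Neither imposes a stop.

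**2. Does any text widen the 9.3 term?** No. Sections 7.2, 7.3 and 7.4.1 speak of the investigational drug, agent and product respectively. The term in 7.3 can be read to include the DMSO-containing product but does not clearly include scraping. Section 9.3 uses the narrowest term, and nothing links it to the others.

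**3. Could an event be attributed to something other than cells?** For a local event at the control site, yes. The clinicians know which site that is; section 4.1.1 says: "It will be impossible to blind the clinicians since they will be injecting the cells versus vehicle". The sites are also well separated: "The injection sites will be spaced at least 5 cm from the center of any neighbor" (5.2.4). A local reaction there can be judged unrelated, or unlikely to be related, to cells placed elsewhere.

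**4. Control-site exposure ceilings.** Inputs: 20 subjects in Phase One and 80 in Phase Two (4.1); one control-site injection per Phase One subject; at most 4 per Phase Two subject; DMSO at up to 10% not more than 3 times (5.2.4), read here as a limit per site.

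- Phase One, vehicle: 20 × 1 = 20.
- Phase Two, vehicle or DMSO: 80 × 4 = 320.
- Of these, 10% DMSO: at most 80 × 3 = 240. If all 320 were given, at least 320 − 240 = 80 would be vehicle.
- Both phases: 20 + 320 = 340, of which at least 20 + 80 = 100 would be vehicle at the full ceiling.

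If the limit of 3 applies per subject across all sites, 240 remains an upper bound.

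**5. Injections left out of the count.** Cell-free injections into the two Phase Two sites that already hold cells could reach 80 × 2 × 3 = 480. A possible relation to cells would usually be conceded there, so 9.3 would usually apply.

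**6. Scraping occasions.** In the text, scraping may occur at injection visits 3 to 6 (days 30, 37, 42, 59) and monitoring visits 7 to 11 (days 42, 70, 98, 126, 154): 4 + 5 = 9 visits. Day 42 appears twice, so there are 8 distinct nominal days. The Phase Two table has 4 injection and 4 monitoring visits before the removal visit: 8 visits on the same 8 days. The size of the scraped subset is not stated.

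**7. DMSO concentration.** 10% / 5% = 2.

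All counts are ceilings. Subjects whose cells fail are discharged before injection (4.4.1), and the later injections and the scraping are optional. The documents give no serious-event rate, so the number of events falling outside 9.3 cannot be derived.

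**The case against.** The strongest reply is that the uncovered case is remote and already watched. It needs an event that meets the serious definition in 7.1.2 and is judged not even possibly related to cells, in a subject who carries cells. The exposures are less than 1 ml of injectate or two gentle strokes of a blade or curette. For a systemic event, a possible relation to cells would usually be conceded. Every serious event reaches the IRB, the FDA and the Safety Monitor, and the investigator who gives the injections can simply stop giving them. All of this stands, and it is why the point is minor. It does not close the gap: the sponsor chose an automatic pause for cell-related events on top of these same channels, and left the other test interventions to discretion.

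A second reply is that 9.3 matches the primary objective. This also stands. A reader might infer that, because safety and tolerability are primary, the rule had to cover everything done at the sites. The documents do not support that: section 2 and section 9.2.1 tie the primary objective and outcome to the fibroblasts, and the secondary objective on curette wounding concerns efficacy only. The argument for the change is protection of healthy volunteers.

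A third reply is that any boundary is a judgement, since tattooing, anaesthesia and excision also take place at these sites. That is fair, so the fix should say where the line falls.

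**Conclusion.** The gap is real but narrow, and the point is minor. As written, a serious event attributed solely to vehicle, to the Phase Two DMSO injections or to scraping does not require a pause; stopping is left to the investigator, Safety Monitor, IRB or FDA. The most plausible instance is a local event at the control site.

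Two stronger readings should be avoided. A reader might infer that such an event would go unreviewed or that dosing must continue; section 7.4.2 shows otherwise. A reader might also take 340 control-site injections as a count of expected or unprotected events; it is a ceiling on exposure only.

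The conclusion assumes that the IND and the institutional IRB policy, which the protocol refers to but which were not supplied, contain no further automatic pause.

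**What to change.** In 9.3, replace the reference to the autologous fibroblasts with: *the study product (autologous fibroblasts, vehicle or DMSO injection) or skin scraping*. In 7.3, add one sentence stating that attribution is judged against that same set.

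State also that events due to biopsy, local anaesthetic, blood draw, tattooing or graft excision stay outside the automatic trigger and remain with the Safety Monitor, IRB and FDA. This keeps the rule from being set off by routine procedures.

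The cost is a phrase in 9.3, a sentence in 7.3 and a line on exclusions. The downside is a slightly higher chance of a pause. No change to sample size, visits or analysis is needed.
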